7.3 Randomization

Patients will be randomly allocated to either active or placebo treatment at their Baseline visit, in Period 1 if they enter in Period 1, or in Period 2 if they enter in Period 2. Patients who participate in both periods will receive the same treatment in Period 2 as they were randomized to receive in Period 1.

8 METHODS OF ASSESSMENT AND ENDPOINTS

8.1 Prescreening Assessments

Blood samples will be taken at the prescreening visit to enable patient eligibility assessment using a 2-step assay.

The assay will be validated and performed at Asuragen, Inc., Austin, Texas, or other subsidiary laboratories working under the Sponsor and Asuragen's close supervision. In step 1 of the assay, HD patient blood samples would undergo 2 independent allele-specific long-range polymerase chain reaction (AS LR-PCR) reactions. Each reaction has primer pairs specific to the SNP3 variant with nucleotides adenine (A) or guanine (G). Amplicons generated from each AS LR-PCR will proceed independently to step 2 of the assay. In step 2, CAG trinucleotide repeat length will be enumerated using Asuragen's AmplideX® PCR/capillary electrophoresis (CE) HTT Kit, which is based on repeat primed polymerase chain reaction (RP-PCR) technology and tested on a genetic analyzer within the terms of its CE mark. The amplicons from each reaction resultant from step 1 will be used for enumerating CAG repeat lengths on wtHTT and mtHTT alleles (also referred to as "phasing").

Only samples from AS LR-PCR with primer pair capable to amplify nucleotide "A" at SNP3 position and, when further analyzed in step 2, the amplicon is shown to be only mutant HTT allele with required CAG repeat length will be identified as phased eligible.

Patients confirmed to carry the A isoform of SNP3 on the same allele as the pathogenic CAG expansion will be qualified to undergo further screening for confirmation of eligibility. Investigators and patients will be advised only as to whether the patient meets the prescreening criteria and will not be provided with specific genetic test results (e.g., number of CAG repeats).

All blood samples will be sent to central laboratories for processing, analysis, and verification. All biological material will be stored and secured in a way that ensures that unauthorized access is prohibited and the samples are not lost, deteriorated, or destroyed accidentally or illegally. Detailed instructions on sample collection, storage, processing, and shipping will be provided in the Laboratory Manual.

8.2 Safety Assessments

The safety assessments will include the following:

- Adverse events ([Section 9](#))
- Medical history and demographics
- Prior and concomitant medications
- Physical examination (including neurological and psychiatric)
- Height and weight
- Vital signs
- 12-lead ECG
- Clinical laboratory evaluations (including clinical chemistry, hematology, and urinalysis)
- Cerebrospinal fluid safety laboratory evaluation
- Suicidality assessment
- Pregnancy testing (if applicable)
- Drug screening

Any abnormal laboratory test results (hematology, clinical chemistry, or urine) or other safety assessments (e.g., vital sign measurements) that are clinically significant in the medical and scientific judgment of the Investigator are to be recorded as AEs or SAEs.

8.2.1 Medical History and Demographics

A general medical history will be obtained at the Screening Visit. Investigator assessment of past medical history at Screening will include information regarding any significant medical, surgical, psychiatric, and/or neurological conditions and treatments.

Prior HD treatments received, and other details about this condition will be recorded. In addition, education level will be recorded in accordance with the International Standard Classification of Education (1997).

Demographic data will be collected and summarized for each treatment group.

8.2.2 Prior and Concomitant Medications

Medications with a start date before the first dose of study drug will be classified as prior medications. Any medication that the patient began taking after the first dose of study drug will be classified as concomitant. Any medication that a patient started before the first dose of study drug and continued to take during the study will be classified as both prior and concomitant. Any medication that was stopped on the same day as the first dose of study drug will be considered a prior medication. If the stop date of a given medication is missing, then the medication will be classified as concomitant.

The minimum requirement is that the drug name, dose, indication, and the dates of administration are to be recorded. This will include all prescription drugs, herbal products, vitamins, minerals, and over-the-counter medications. Any changes in concomitant medications will also be recorded in the patient's eCRF.

Any concomitant medication deemed necessary for the welfare of the patient during the study may be given at the discretion of the Investigator. However, it is the responsibility of the Investigator to ensure that details regarding the medication are recorded in full in the eCRF.

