4.3 Study Endpoints

Safety

Adverse events, concomitant medications, physical examinations including detailed neurological examination, vital signs, weight, 12-lead electrocardiograms (ECGs), clinical laboratory evaluations (including clinical chemistry, hematology, and urinalysis), CSF safety evaluations, MRI of the brain, and Columbia-Suicide Severity Rating Scale (C-SSRS)

Pharmacokinetics

- Pharmacokinetic parameters of WVE-003 in plasma at predefined time points
- Concentration of WVE-003 in CSF at predefined time points

Pharmacodynamics

- Change from baseline in the level of mHTT protein in CSF
- Change from baseline in the level of tHTT protein in CSF
- Change from baseline in the level of wtHTT protein in CSF
- Change from baseline in the level of NfL in CSF
- Change from baseline in the level of exploratory biomarkers in CSF, plasma, and/or PBMCs

Clinical Effects

- Change from baseline in the UHDRS Total Functional Capacity (TFC)
- Change from baseline in UHDRS total motor score
- Change from baseline in the UHDRS independence scale
- Change from baseline in Symbol Digit Modalities Test (SDMT)
- Change from baseline in Stroop word reading test
- Change from baseline in the composite UHDRS
- Change from baseline in the PBA-s
- Changes from baseline in MRI of the brain

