4.4.3.3 Individual Stopping Criteria

Dosing will be stopped for an individual patient at any time in the study if:

- A patient experiences a serious or intolerable adverse event (AE) that, in the Investigator's opinion, requires study drug discontinuation.
- A patient experiences a TEAE that is severe in intensity and related to administration of WVE-003 (except TEAEs associated with lumbar puncture).

The patient will be followed up for safety per protocol. Per the Investigator's judgement, the patient may be allowed to resume participation in the study if or when the event has resolved]. Dosing may be resumed for individual patients upon recovery from the severe event and if supported by the Investigator, based on their assessment of the benefit/risk balance for the patient.

4.4.3.4 *Adverse Events That are Exempt from Stopping Criteria*

Intrathecal administration of drugs is known to result in untoward effects such as post-lumbar puncture headache, pain, etc.^{33,34} Given the common occurrence of such side effects following lumbar puncture, it is anticipated that patients may experience AEs temporal to the IT administration procedure that are not attributable to study drug^{33,34}. Therefore, the AE terms listed in [Table 5](#) will be exempted from the assessment of Stopping Criteria:

Table 5 Adverse Event Preferred Terms Exempted From Stopping Criteria

Preferred Terms Exempt From Stopping Criteria	
Administration site bruise	Instillation site bruise
Catheter site bruise	Post-lumbar puncture syndrome
Infusion site bruising	Post-procedural discomfort
Infusion site discomfort	Post-procedural contusion
Infusion site pain	Procedural headache
Injection site bruising	Procedural pain
Injection site discomfort	Traumatic lumbar puncture
Injection site pain	

Abbreviations: AE = adverse event; MedDRA = Medical Dictionary for Regulatory Activities; PT = Preferred Term.

Note: AEs exempted from the Stopping Criteria include the MedDRA PTs listed above and their associated verbatim terms.

While these procedural events are exempt from Stopping Criteria review, they will be recorded as AEs as described in [Section 9](#). In addition, as part of their ongoing review of unblinded safety data, the SMC will carefully review the above-referenced exempted AE terms to ensure there are no meaningful imbalances between treatment groups.

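### Section 8.2.2 gives two conflicting classes, with no precedence, for a medication started after the first injection and stopped the same day, so Day 1 treatments can drop out of the concomitant-medication endpoint

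*Combined protocol and SAP*

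**What the plan says.** Section 8.2.2 sets out its classification in one paragraph. In order, the rules that matter here are:

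- Start before: "Medications with a start date before the first dose of study drug will be classified as prior medications".
- Start after: "Any medication that the patient began taking after the first dose of study drug will be classified as concomitant". There is no condition on the stop date.
- Dual class: a drug that was started before the first dose and that the patient "continued to take during the study will be classified as both prior and concomitant".
- Same-day stop: "Any medication that was stopped on the same day as the first dose of study drug will be considered a prior medication". There is no condition on the start time.
- Missing stop date: concomitant.

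On the data to be collected, the same section says "The minimum requirement is that the drug name, dose, indication, and the dates of administration are to be recorded". Clock time is not part of that minimum.

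Section 4.3 opens its list of safety endpoints with "Adverse events, concomitant medications, physical examinations including detailed neurological examination", so concomitant medication is a listed safety endpoint. The footnotes to Table 1 keep every patient in clinic until the day after the dose, with medications recorded during that time. Section 11.3.4 starts the on-treatment adverse event window at the first dose.

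**The concern.** Each of the two sentences is clear alone, but they overlap. A single analgesic given two hours after the Day 1 injection starts after the first dose, which makes it concomitant. It also stops on the first-dose day, which makes it prior. Two programmers could each follow Section 8.2.2 and produce different tables from the same data.

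The records in question bear on acute tolerability. The primary objective is safety and tolerability, and Section 2 justifies placebo lumbar punctures by the need to tell drug effects from procedure effects. A treatment given in the hours after the injection is relevant to that question. If it is labelled prior, a Day 1 headache would be reported as treatment-emergent while the drug given for it would be reported as pre-treatment.

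A second gap sits beside the first. Section 11 plans separate analyses for Period 1 and Period 2, but Section 8.2.2 does not say whether the first dose means the first in the study or the first in the period. For rollover patients these are different days.

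**Working it through.** No figure in the plan needs reproducing, so the check applies the Section 8.2.2 rules to each start and stop pattern around the first injection.

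| Pattern | Start | Stop | Rules met | Class |
|---|---|---|---|---|
| a | before Day 1 | Day 1 | start before; same-day stop | prior, no conflict |
| b | Day 1, before the injection | Day 1 | same-day stop | prior, no conflict if the start time is known |
| c | Day 1, after the injection | Day 1 | start after; same-day stop | concomitant and prior, conflict |
| d | after the injection | Day 2 or later | start after | concomitant, no conflict |
| e | after the injection | missing | start after; missing stop date | concomitant, no conflict |

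Only pattern c is affected. The dual class does not rescue it, because that class is defined for drugs started before the first dose.

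Size of the loss: let n be the number of pattern c records and k the number of them left out of the concomitant count. The loss is k / n.

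- Start-after rule prevails, or both labels are applied: k = 0, so the loss is 0 / n = 0%.
- Same-day-stop rule prevails as an exclusive label: k = n, so the loss is n / n = 100%.

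The documents give no rate of Day 1 medication use, so n is unknown and no absolute undercount can be computed.

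Data available: with dates alone, patterns b and c give the same record (start Day 1, stop Day 1). The start-after rule then cannot be applied reliably, because the record does not show on which side of the injection the drug began. The same-day-stop rule needs only a date. Adverse events are better placed, since Section 9.1 collects their onset date and time.

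Scope in time: the same-day rule is tied to the first-dose day. The Week 8 and Week 16 dosing days in Period 2 Cohort 1 are not touched by it.

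Period 2 reference: take a one-day drug given after the injection on Period 2 Day 1. If first dose means first in the study, the record is pattern c for a new patient, but plainly concomitant for a rollover patient, whose first dose was in Period 1. If it means first in the period, the record is pattern c for both. Section 11.3 fixes a Period 2 reference for clinical effects and pharmacodynamic baselines. It does not do so for medications.

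**The case against.** The strongest reply is that the same-day sentence directly follows the one on drugs started before the dose and continued. In that position it can be read as the boundary for those drugs: ended on Day 1 means not continued. It also does not say that the drug is prior only, and the paragraph allows some drugs to carry both labels. On that reading nothing is lost. This stands as a plausible intention, and it is why the loss cannot be stated as certain. It does not remove the defect, because the sentence as written covers any medication and no precedence is given.

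Other mitigations also stand. Section 9.1 has each adverse event record carry any treatment required. Section 11.3.4.1 summarizes events related to drug or to procedure. Section 4.4.3.4 has the safety monitoring committee look for imbalance in the exempted procedural terms. The medication record itself remains in the eCRF, so a label is at stake and no data are lost. The rule applies equally in both arms.

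A reader might infer three stronger points that the documents do not support:

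- That the plan's drug-versus-placebo comparison of medication use is biased. Section 11 specifies no concomitant-medication summary, so there is no stated comparison to bias.
- That the protocol expects one-day treatments to be common. Section 4.4.3.4 says "Intrathecal administration of drugs is known to result in untoward effects such as post-lumbar puncture headache, pain" and calls such side effects common. It says nothing about how often they are treated or whether treatment is confined to Day 1.
- That new and rollover patients will in fact be classed differently in Period 2. That follows only under one reading of an undefined term.

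**Conclusion.** The point holds as a conflict between two written rules within a listed safety endpoint. For a medication started after the first injection and stopped the same day, Section 8.2.2 gives both classes and no way to choose. The effect is 0% to 100% of such records, the upper end requiring that the same-day-stop sentence be applied as an exclusive label. Their number is not stated, and it could be small.

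It would be tempting to conclude that these treatments are already classed as pre-treatment and that the endpoint therefore undercounts them. The text does not establish that, because the start-after sentence classes the same records as concomitant. An undercount is possible, not certain, and its reach depends on a summary that Section 11 does not describe.

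The point is still more than missing detail. A stated rule, applied literally, gives the wrong class for these records and sits awkwardly with an on-treatment window that opens at the first dose. It is small, and cheap to correct.

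**What to change.** Four changes, all to data classification and none to patient management:

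1. Limit the same-day sentence: a medication begun before the first dose and ended on the first-dose day is prior only.
2. State that any medication begun after the first dose is concomitant, whatever its stop date.
3. For medications on a dosing day, use the start time or a before/after-dose flag where available. Where the timing is unknown, class the record as concomitant.
4. For the separate Period 2 analysis, use the first Period 2 dose as the reference for new and rollover patients alike.

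The cost is a change of wording in Section 8.2.2 and, going forward, one flag in the eCRF. The flag cannot be relied on for patients already dosed. The notes to Figure 1 show 11 + 6 + 6 = 23 Period 1 patients in the data already reviewed by the committees, and the required minimum for their medications was dates. Under the default in item 3, some pre-dose drugs taken only on Day 1, including in those patients, will count as concomitant. That small overcount is the price of not dropping postdose treatment, and a footnote to the table can state it.

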8.2.3 Physical Examination

A complete physical examination will be performed at the time points noted in the Schedule of Assessments. The physical examination will include (but is not limited to) an examination of the head, eyes, ears, nose, throat, respiratory, cardiovascular, gastrointestinal, musculoskeletal, psychiatric, and neurologic systems, and neurologic (including mental status, cranial nerves, motor system, reflexes, coordination and gait, and sensory system) systems.

At the postdose time points noted in the Schedule of Assessments, a targeted physical exam to assess potential motor effects will be performed. This exam will include a neurologic examination with special attention to the motor system, upper and lower extremity measures of strength, tone, reflexes, and ambulation.

Physical findings will be recorded in the eCRF and source documents.

8.2.4 Height and Weight

The patient's height and weight will be measured at the time points described in the Schedule of Assessments and recorded in the eCRF and source documents.

8.2.5 Vital Signs (Blood Pressure, Heart Rate and Temperature)

Vital sign measurements will be taken as per standard site practice, after the patient has been resting quietly (either lying flat or sitting, whichever is most appropriate for the condition of the patient) for a period of at least 3 minutes. Blood pressure (systolic and diastolic), temperature, and pulse will be measured by medically qualified personnel at the time points described in the Schedule of Assessments and recorded in the eCRF and source documents. As feasible, the same

position (either sitting or lying) should be used for all subsequent blood pressure measurements during the study for an individual patient. If the initial reading is high, the measurements will be repeated twice, and the average of the 3 readings will be used.

8.2.6 12-Lead ECG

Computerized, good quality, 12-lead ECGs will be collected and recorded at the time points described in the Schedule of Assessments. Recordings will be obtained in the *supine* position after the patient has rested comfortably for ≥ 10 minutes.

The ECG tracing will be submitted and read by a centralized reviewer (details will be provided in a study-specific manual). The following should be recorded on the trace and eCRF: whether the ECG is normal or abnormal and, if deemed abnormal, whether the abnormality is clinically significant or not clinically significant and note the abnormality.

8.2.7 Clinical Laboratory Evaluations

Clinical laboratory safety testing will be collected at the time points described in the Schedule of Assessments and recorded in the eCRF and source documents. Safety laboratory samples will be analyzed at a central laboratory. Local testing on these samples may be conducted as clinically indicated.

The parameters to be assessed are presented in [Table 6](#). The full panel should include all parameters listed. Specific time points, as specified in the Schedule of Assessments, only require complete blood count (CBC), C-reactive protein (CRP), , complement, and fibrinogen.

Table 6 Clinical Laboratory Assessments

Hematology	Coagulation	Clinical chemistry	Urinalysis

Complete blood count, including:
 
• White blood cell count (with differential when values are abnormal)• Red blood cell count• Hemoglobin• Hematocrit• Platelet count• Reticulocyte count• Mean corpuscular volume• Mean corpuscular hemoglobin• Mean corpuscular hemoglobin concentration 
Measures of Inflammation, including:
 
• High Sensitivity C-reactive protein• Complement• Fibrinogen	Activated partial thromboplastin time Prothrombin time International normalized ratio	Sodium Potassium Chloride Bicarbonate Blood urea nitrogen Creatinine Creatine phosphokinase Alanine aminotransferase (ALT) Aspartate aminotransferase (AST) Alkaline phosphatase Bilirubin	Urinalysis

8.2.8 Cerebrospinal Fluid Safety Laboratory Evaluation

A CSF safety laboratory sample obtained at the times noted on the Schedule of Assessments will be evaluated at a local laboratory. All CSF samples should be collected using an atraumatic needle. The following parameters will be assessed: total protein, glucose, and cell counts and differential per local laboratory specifications.

Samples will only be used by the Sponsor and/or a contracted vendor for research related to the development of treatments for HD and stored for a maximum of 10 years. All biological material will be stored and secured in a way that ensures that unauthorized access is prohibited and the samples are not lost, deteriorated, or destroyed accidentally or illegally. Detailed instructions on sample collection, storage, processing, and shipping will be provided in the Laboratory Manual.

8.2.9 Suicidality Assessment (Columbia-Suicide Severity Rating Scale)

The C-SSRS is a measure of suicidal ideations and suicidal behaviors³⁵. The C-SSRS, provided in the Study Manual, consists of 2 forms: a form measuring symptoms at Screening (baseline/screening version) that includes a lifetime history and a form measuring symptoms since the last study visit (“since last visit” version). The baseline/screening form will be performed at the Screening visit, and the “since last visit” form will be performed at all later time

points, as described in the Schedule of Assessments. A trained rater will complete this scale. The findings should be confirmed by the clinical opinion of the Investigator.

The Investigator should be notified if a patient responds “yes” to any of the questions. The Investigator will provide care according to local standards, which may include referral to specialists, medical treatment, or hospitalization as necessary.

8.2.10 *Pregnancy Testing*

For female patients of childbearing potential, a negative serum pregnancy test must be documented at the Screening Visit, and a negative urine pregnancy test must be documented at the times noted on the Schedule of Assessments. The serum pregnancy test will be determined by a central laboratory; urine pregnancy tests will be performed locally.

8.2.11 *Drug Screening*

A urine drug screen for opioids, cocaine, amphetamines, methadone, barbiturates, methamphetamine, and phencyclidine will be performed at the times noted on the Schedule of Assessments. Drug screen tests will be evaluated by a central laboratory.

8.3 *Pharmacokinetic Assessments*

Cerebrospinal fluid as well as plasma and urine samples for analysis of exposure to WVE-003 will be collected at the time points specified on Schedule of Assessments. Samples will be collected at the following time points:

Period 1 Plasma PK: Samples will be collected at all clinic visits during the Period 1 treatment phase. On Week 0/Day 1, samples will be collected predose (within 4 hours prior to dosing), and postdose at 30 minutes (± 5 minutes), 1 hour (± 15 minutes), 2 hours (± 15 minutes), 4 hours (± 30 minutes), 6 hours (± 30 minutes) and 24 hours (± 2 hours) postdose. On all clinic visits (Week 2, Week 4, Week 8, and Week 12), samples will be collected. A sample will also be collected at the early termination (ET) visit, if the patient discontinues early.

Period 1 Urine PK: Samples will be collected on Week 0/Day 1 from 0-4 hours, 4-8 hours, and 8-24 hours postdose.

Period 1 CSF PK: Samples will be collected predose on Week 0/Day 1, as well as Week 2, Week 4, Week 8, and Week 12. A sample will also be collected at the ET visit, if the patient discontinues early.

Period 2 Plasma PK: At the first and last dosing visit, blood samples will be collected predose (within 4 hours prior to dosing), and postdose at 30 minutes (± 5 minutes), 1 hour (± 15 minutes), 2 hours (± 15 minutes), 4 hours (± 30 minutes), and 6 hours (± 30 minutes). New patients only will also have a sample collected on Day 1 at 24 hours (± 2 hours) postdose. For any other dosing visit, blood samples will be collected at 2 hours (± 1 hour) postdose. In addition, plasma PK samples will be collected once at all non-dosing clinic visits. A sample will also be collected at the ET visit, if the patient discontinues early.

Period 2 CSF PK: Samples will be collected at all clinic visits (Week 0/Day 1, Week 4, Week 8, Week 12, Week 16, Week 20, Week 24, and Week 28). The sample will be collected predose on dosing visits. A sample will also be collected at the ET visit, if the patient discontinues early.

The date and time of the sample collection will be recorded.

Samples will be analyzed by a central laboratory to determine concentrations of WVE-003 using validated methods (plasma and CSF) or qualified methods (urine).

Samples will only be used by the Sponsor and/or a contracted vendor for research related to the development of treatments for HD and stored for a maximum of 10 years. All biological material will be stored and secured in a way that ensures that unauthorized access is prohibited and the samples are not lost, deteriorated, or destroyed accidentally or illegally. Detailed instructions for sample collection, storage, processing, and shipping will be provided in the Laboratory Manual.

